3 STUDY SCHEMA

4 SCHEDULE OF ACTIVITIES

Table 1. Schedule of Events for Screening and Enrollment, AURYON atherectomy Procedure and Post-Procedure Follow-up

Study assessment	Pre-Procedure	Procedure	Post-procedure	Hospital discharge	30 Days (±1 weeks)	6, 12, 24 Months (±1 Month)
Medical history & demographics	X					
Physical Examination	X					X
Informed Consent	X					
Angiographic evaluation of target lesion	X	X	X			
PAD Intervention including AURYON Atherectomy		X				
Quantitative DUS						X
ABI ⁰	X					X
Rutherford Classification	X					X
WIQ	X					X
Record of relevant medications ¹	X	X		X	X ³	X ⁴
Record of PPMAEs ² and other procedural complication		X	X	X		
Record of MAEs ²					X ³	X ⁴

⁰ Toe-brachial index (TBI) will be taken for subjects with non-compressible vessels

¹ Relevant medications: anticoagulant and anti-platelets.

² Adverse events should only be captured after signing of the Informed Consent Form.

³ The visits may be done via phone call for record of any reportable adverse events and relevant medications.

⁴ In case that subject is not showing up to one or more of these follow-up visits, the site should contact the subjects by telephone to collect as much data as possible of any reportable adverse events and relevant medications.

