	
assessed quantitatively by Duplex ultrasonography (DUS); OR, (2) for BTK lesions: freedom from occlusion (100% stenosis by DUS) combined with freedom from CD-TLR, at 6, 12, and 24 months.
 
4. Clinical outcomes, defined as change in ankle brachial index (ABI or TBI if needed), walking impairment questionnaire (WIQ), and Rutherford category at 6, 12, and 24, months, compared to baseline
 
Exploratory endpoint(s):
 
1. Intravascular ultrasound assessment pre- and post-Auryon and correlation with angiographic findings (e.g. lesion length, MLA -minimal lumen area gain, calcium severity and removal, etc.). This endpoint will be analyzed only for cases that used IVUS as a routine practice in the index procedure.

STUDY POPULATION:	
Patients with infra-inguinal PAD undergoing atherectomy with the AURYON Atherectomy System.
 
Inclusion Criteria A potential subject will be included in the study if he/she meets all the following inclusion criteria:
 
 1. Subject is ≥ 18 years old. 2. Subject is a candidate for atherectomy for infra-inguinal peripheral artery disease. 3. Documented symptomatic atherosclerotic peripheral artery disease with claudication or critical limb ischemia (CLI) (Rutherford Classification 2-5). 4. Subject is capable and willing to comply with the scheduled follow up 5. Subject is able and willing to sign a written Informed Consent Form (ICF). 
Exclusion Criteria A potential subject will be excluded from the study if he/she meets any of the following exclusion criteria:
 
 1. Target lesion is in an arterial bypass. 2. Planned use of another atherectomy device in the same procedure 3. Co-morbid condition(s) with less than 1yr anticipated survival that could limit the subject's ability to participate in the trial or to comply with follow-up requirements or impact the scientific integrity of the study.

	4. Participating in another study on an interventional non-cleared device, that could impact the study results

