DESCRIPTION OF SITES/FACILITIES ENROLLING PARTICIPANTS:	
This study will be conducted at sites where eligible PAD patients are routinely treated with atherectomy by AURYON Atherectomy System.
 
Total enrollment of approximately 100 subjects at approximately 10 sites in the US.
 
To reduce bias by sites, each site may enroll up to 15 eligible subjects whom have successfully completed their index atherectomy treatment with the AURYON system and with analyzable imaging for the primary efficacy analysis.

DESCRIPTION OF STUDY PROCEDURE:	Atherectomy by the AURYON system, of infra-inguinal stenoses, occlusions or in-stent restenosis (ISR).
STUDY DURATION:	The study duration is expected to be two and a half (2.5) years: 6 months to enroll and two (2) years to follow up all subjects.
PARTICIPANT DURATION:	Two (2) years
PRIMARY ANALYSIS PLAN:	
As this is a pilot registry study, no formal hypotheses are defined; rather statistical analyses will be descriptive in nature and will serve to provide estimates of the primary and secondary study endpoints.
 
Also, no formal sample size calculation was performed. The number of enrolled subjects will allow for sufficient safety monitoring and evaluation of the safety and efficacy endpoints and will provide point estimates for the large-scale registry.
 
Analysis sets:
 
Intent-to-treat (ITT) population: The intent-to-treat (ITT) population will consist of all subjects who signed the informed consent form and underwent procedure with an attempt of using the AURYON system.
 
Modified Intent-to-treat (mITT) population: The modified Intent-to-treat (mITT) population will consist of all ITT subjects who underwent atherectomy using the AURYON system for at least one lesion.
 
Per-protocol (PP) population

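### The telephone fallback for missed 6-, 12- and 24-month visits leaves out WIQ, so its change from baseline is an available-case estimate at each visit

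*Combined protocol and SAP*

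**What the plan says.** Secondary endpoint 4 (Section 2, Protocol Summary) is the change in ankle-brachial index (or toe-brachial index where needed), "walking impairment questionnaire (WIQ), and Rutherford category at 6, 12, and 24, months, compared to baseline".

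Table 1 (Section 4, Schedule of Activities) schedules WIQ before the procedure and at the 6-, 12- and 24-month visits, which have a window of one month either side. The WIQ cell for those visits is a plain X. In that column only the rows for relevant medications and for MAEs carry footnote 4.

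Footnote 4 begins "In case that subject is not showing up to one or more of these follow-up visits" and continues "the site should contact the subjects by telephone to collect as much data as possible of any reportable adverse events and relevant medications". Footnote 1 defines the second item: "Relevant medications: anticoagulant and anti-platelets".

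On analysis, the Primary Analysis Plan in Section 2 says that "statistical analyses will be descriptive in nature and will serve to provide estimates of the primary and secondary study endpoints". Secondary endpoints are analysed in the mITT and PP populations, both of which are defined by what happened at the procedure. No method for missing follow-up values accompanies this.

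**The concern.** Most of the follow-up assessments need the subject to be present. Duplex ultrasound and ABI do, and Rutherford category does at least in part. WIQ is a questionnaire, so it is the item that a telephone call could most plausibly recover. The plan already directs sites to call these subjects, but the list of what to collect leaves WIQ out.

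An absentee stays in the mITT and PP populations but contributes no WIQ value at that visit, so the reported mean change describes those who attended. Attendance at a clinic could well be related to walking ability in a population that runs from claudication to critical limb ischemia (Rutherford 2–5). If it is also related to the change in walking ability, the estimate is biased. The pilot exists to supply estimates for a registry of about 1000 patients. A selection bias does not shrink as the sample grows, so the same schedule carried forward would give the same bias with a narrower interval.

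**Working it through.** **Step 1: what the text allows.** The instruction to collect what can be collected is limited by the list that follows it, namely reportable adverse events and relevant medications. The second item means anticoagulants and antiplatelets, so WIQ cannot be read into it. The placement of the footnote agrees: the WIQ row does not carry it. Followed as written, the schedule yields no WIQ for a missed visit.

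**Step 2: what kind of estimate results.** A subject who misses 6 months can still contribute at 12 or 24 months. With no stated imputation or model, the estimate at each visit uses whoever has a value then, which is an available-case estimate per visit.

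**Step 3: inputs.** There is no figure in the plan to reproduce, since "no formal sample size calculation was performed".
- N = 100, from Section 2: "Total enrollment of approximately 100 subjects at approximately 10 sites in the US".
- m, the share missing a visit: assumed 10%, 20% or 30%.
- d, attendees' mean change in WIQ minus absentees' mean change: assumed 5, 10 or 15 points. This is a difference in change from baseline, not in walking level.
- r, the share of absentees reached by telephone, taken as a random share of them: assumed 50% or 80%.

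**Step 4: bias and precision without telephone WIQ.** The mean over all subjects is (attendees' mean) − m × d, so the available-case bias is m × d. The standard error grows by √(1/(1 − m)). The 95% half-width, in SD units of the change, is 1.96/√n, which is 0.196 at n = 100.

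| m | n with WIQ | Bias, d = 5 | Bias, d = 10 | Bias, d = 15 | SE factor | Half-width (SD) |
|---|---|---|---|---|---|---|
| 10% | 90 | 0.5 | 1.0 | 1.5 | 1.05 | 0.207 |
| 20% | 80 | 1.0 | 2.0 | 3.0 | 1.12 | 0.219 |
| 30% | 70 | 1.5 | 3.0 | 4.5 | 1.20 | 0.234 |

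If d = 0 the bias is zero. If d is negative the sign reverses: d = −5 gives −0.5 to −1.5 points.

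**Step 5: what a call would leave.** With a random share r recovered, absentees make up m × r/(1 − m(1 − r)) of those with a value, and the remaining bias is m × d × [1 − r/(1 − m(1 − r))].
- m = 10%, d = 5: 0.5 × (1 − 0.5/0.95) = 0.24 points at r = 50%; 0.5 × (1 − 0.8/0.98) = 0.09 at r = 80%.
- m = 30%, d = 15: 4.5 × (1 − 0.5/0.85) = 1.85 points at r = 50%; 4.5 × (1 − 0.8/0.94) = 0.67 at r = 80%.

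Under these assumptions, reaching half of the absentees removes rather more than half of the bias. A mode effect, or a difference between absentees who can be reached and those who cannot, would alter these figures.

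**The case against.** The case against is substantial, and much of it stands.

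- **Direction.** A reader might infer that WIQ change is biased toward improvement. The documents do not support that. They give no attendance rates or reasons for absence, and subjects who feel well may also skip visits. The worst walkers may have been the worst at baseline and changed just as much, in which case d = 0.
- **Type of analysis.** A reader might infer a completer analysis. The plan names none, and its analysis sets do not depend on attendance. The text reviewed ends with Section 4, so a missing-data section elsewhere cannot be excluded, although it would not restore answers that were never collected.
- **Strength of the instruction.** Footnote 4 says that sites should call. It does not guarantee that contact is made. It does not forbid asking WIQ, and the one-month window allows rescheduling. WIQ is therefore lost only when the visit is missed altogether. Even so, a step that is merely not forbidden will be handled differently across about 10 sites.
- **Mode effect.** It is tempting to say that an in-person-only sensitivity analysis deals with it. It does not. Every telephone value would come from an absentee and every in-person value from an attendee, so mode and absence are fully confounded. Whether WIQ is valid by telephone cannot be settled from these documents.
- **Scope.** ABI/TBI, Rutherford category and duplex patency have the same exposure to missed visits, and this change leaves them as they are. WIQ would then rest on a somewhat different set of subjects from the other parts of secondary endpoint 4.
- **Consequence.** This is one component of a secondary endpoint in an unpowered descriptive pilot, and neither primary endpoint is affected.

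None of this alters the textual point: as written, the call omits WIQ and nothing replaces it.

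**Conclusion.** The point holds as a low-cost improvement; the plan contains no error or contradiction here. Following Table 1 as written loses WIQ whenever a 6-, 12- or 24-month visit is missed. The size of any bias rests wholly on assumed values of m and d: the range of 0.5 to 4.5 points has its upper end where both assumptions are at their most unfavourable, and zero or the opposite sign is possible. The documents give no SD or relevant difference for WIQ, so these points cannot be judged large or small. Lost precision is not the reason to act, since the standard error rises by only 5–20%. Telephone collection would recover part of the missing information, not all of it.

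**What to change.** Amend footnote 4 and attach it to the WIQ row, so that WIQ is also administered on the call after a missed 6-, 12- or 24-month visit where the subject can be reached. Add a field for mode of administration. At each visit, report the number with WIQ by mode and the reasons for missing values, and present the change from baseline with and without the telephone values. State that a difference between the two may reflect selection, mode or both.

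The cost is a few minutes on a call that sites are already told to make, one data field and one extra line in each table. The downside is a possible mode effect, which the in-person-only result displays but cannot isolate. Subjects who have died or cannot be reached remain missing, so the reasons for missing values should be read alongside the estimate.
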